### 1.3. Determination of sample size

Sample size determination is based on the two co-primary endpoints: change from baseline to 6 months of the HINT-Q (efficacy assessment), and major complication incidence rate during the 12-month follow-up (safety assessment).

The expected efficacy is an improvement of 50 points at 6 months of device use.

Data on the change from baseline to 6 months are not available in literature, but 2 studies describe the HINT-Q magnitude after 12 months of device use. Waltzman et al. [1] described an increase of 47.7% (SD=26.6%) from pre- to 3 months post-implantation, similar results are reported by Lin et al. [2] with a magnitude of 60% (SD=24.1%) at 12 months. Considering an observed performance plateau around 6 months, we can consider that standard deviation obtained at 3 and 12 months can be used for 6 months of device use in this study. In addition, in the main studies conducted at 6 months, the standard deviation are ranged from 22% to 28%, which is consistent with other results on the change from baseline. Data from literature using the same efficacy assessment criterion provided a weighted average  $\pm$  weighted standard deviation change from baseline of 57.43%  $\pm$  25.05%. Such estimation has been rounded conservatively to 50%  $\pm$  25%.

The sample size required to have 95% chance to get a significant efficacy result assuming a true mean improvement of 50%, a standard deviation of change from baseline of 25% and a type I error of 0.025 (one-sided) is 7 patients. It means that the expected improvement is so large with respect to the variability that the sample size calculation is not driven by efficacy considerations.

As requested by the FDA, the sample size will be set at a total of at least 50 subjects to support the safety. If the incidence rate of major complications is 2% then the chance to observe at least one event is 63.5%. The exact upper limit of the 95% CI will be 10.6% for an observed rate of 2%.

Regarding any complication the expected rate 35%. If the observed rate is 36% then the precision is around 13% in points.

In order to ensure that at least 50 subjects will be implanted with the device, starting with the anesthesia followed by surgery procedure, 55 subjects will be included.

An arbitrary minimum of 39 English speaking patients and 16 non-English-speaking patients will be recruited to meet the FDA requirement. It is possible that the recruitment in a given language be smaller than expected. In this case patients from other languages may replace the shortage provided that a minimum of 5 French speaking patients and 5 Danish speaking patients be recruited to justify the class of language.

## 1.4. Study plan

Protocol activity	V1	V2	V3	V4	V5	V6	V7	V8	Unscheduled visit(s) #
	8 weeks pre-surgery	4 weeks pre-surgery	Baseline	2 weeks post-surgery	1 month post-surgery	3 months post-activation	6 months post-activation	12 months post-activation	
	Screening	Inclusion	Surgery	Follow-up	Activation	Follow up	Follow up	End of study	NA
	Week (-8)	Week (-4)	Week (0)	Week (+2) post-surgery	Month (+1) post-surgery	Month (+4) post-surgery	Month (+7) post-surgery	Month (+13) post-surgery	NA
Eligibility									
Informed consent	X*	X**							
Eligibility criteria		X							
Demographic data		X							
Medical and Hearing History		X							
Evaluations									
HINT-Q		X			X	X	X		
HINT-N		X			X	X	X		
Study device									
Surgery			X						
Implant activation					X				
Patient Diary									
Diary issued					X	X	X		
Diary returned						X	X	X	
Safety									
Adverse event reporting			X	X	X	X	X	X	X
Electrodes Impedance			X		X	X	X	X	(X)
ECAP			X		X	X	X	X	(X)
Concomitant medications		X	X	X	X	X	X	X	X

\*Informed consent given

\*\*Informed consent obtained

# visits may occur in addition to the predefined protocol specific visits. Unscheduled consultations must be related to CI complications/adverse events and/or additional speech processor fittings. The PI may plan any unscheduled consultations as needed. Impedance and ECAP measurements are optional and depend on the nature of patient visit.

Visit	Visit interval (defined as number of weeks relative to visit 3, baseline)	Visit window (defined as number of days from previous visit indicated plus and/or minus day stated)	Visit window (defined as a range in days from previous visit indicated)
1	-8	NA	NA
2	-4	28 days from visit 1 (-25 to +14 days)	3-42 days from visit 1
3	0	28 days from visit 2 (+/- 14 days)	14-42 days from visit 2
4	+2	14 days from visit 3 (-7 to +6 days)	7-20 days from visit 3
5	+4	28 days from visit 3 (-3 to +6 days)	25-34 days from visit 3
6	+16	112 days from visit 3 (-7 to +6 days)	105-118 days from visit 3
7	+28	196 days from visit 3 (-7 to +6 days)	189-202 days from visit 3
8	+52	364 days from visit 3 (-7 to +6 days)	357-370 days from visit 3

## 2. Collected Data

Data will be obtained through 2 types of document: an electronic Case Report Form (eCRF) and a paper Patient Diary. The eCRF will be completed by the investigator at each of 7 visits planned by the protocol (no collected data at the first screening visit V1).

### 2.1. Electronic Case report Form

**Visit 1 (screening, Week -8 pre-surgery):** no data collected, informed consent form given to the patient

#### Visit 2 (inclusion, Week -4 pre-surgery)

- Date of visit
- Date of written informed consent
- Inclusion/exclusion criteria
- Demographic data: birthday, gender, language, vital signs (weight/height)
- Medical history: allergies and significant medical history
- Concomitant medications
- Etiology: age at onset of hearing loss, age of first used hearing aid, age at onset of severe to profound hearing loss (for each ear), vertigo, tinnitus
- Diagnostic imaging: CT scan, MRI exam and exam
- Audiometric evaluations: HINT-Q, HINT-N
- Audiometric evaluations in routine care shall be recorded, if available
- Cochlear implantation scheduling date

#### Visit 3 (implantation, Week 0 surgery)

- Date of surgery
- Type and time of surgery, surgical approach
- Objective measures: impedance and ECAP test
- Presence of adverse events
- Modification of concomitant medications

- Adverse events

#### **Visit 4 (follow-up, Week +2 post-surgery)**

- Date of visit
- Clinical examination: general state, scarring, skin-flap assessment
- Presence of adverse events
- Modification of concomitant medications

#### **Visit 5 (activation, Month +1 post-surgery)**

- Date of activation
- Objective measures: impedance and ECAP test
- Delivery of Patient Diary with instructions to use it
- Presence of adverse events
- Modification of concomitant medications

#### **Visit 6 and 7 (follow-up, Month+3 and Month+6-surgery)**

- Date of visit
- Audiometric evaluation: results of HINT-Q and HINT-N tests
- Audiometric evaluations in routine care, if available
- Objective measures: impedance and ECAP test
- Respect of stimulation duration assessed through the patient diary
- Presence of adverse events
- Modification of concomitant medications

#### **Visit 8 (end of study, Month +12 surgery)**

- Date of visit
- Completion of study and reason of discontinuation
- Audiometric evaluation: results of HINT-Q and HINT-N tests
- Audiometric evaluations in routine care, if available
- Objective measures: impedance and ECAP test
- Respect of stimulation duration assessed through the patient diary
- Presence of adverse events
- Modification of concomitant medications

#### **Unscheduled visit**

- Date of visit
- Reason of visit
- Objective measures: impedance and ECAP test
- Modification of concomitant medications
- Presence of adverse events

## 2.2. Patient Diary

Patient must indicate in the Patient Diary for each day the duration of the stimulation (in hours) and the reason why the duration has not been respected (battery, sound issues, other reason).

At visits 6, 7 and 8, the investigator will review this Patient Diary and indicate in the eCRF all days without respected stimulation duration (less than 8 hours/day).

## 3. General statistical approach

The quantitative variables will be summarized using the following parameters:

- Number of missing and non-missing data,
- Mean and Standard deviation,
- 2-sided 95% Confidence Interval (CI) of the mean,
- Median, minimum and maximum.

The qualitative variables will be summarized using the following parameters:

- Number of missing and non-missing data,
- Counts and percentages with 2-sided 95% CI.

Statistical analysis will be performed at the 5% global significance level using 2-sided tests.

Statistical tests will be chosen according the type of variable:

By default, missing data or unknown responses will not be counted in the denominator of percentages but will be presented in the results tables.

Handling of missing data:

- Rule 1: If the assessment at M6 is missing but a further assessment is available, the missing assessment will be replaced by the next available data.
- Rule 2: If the assessment at M6 and M12 are missing but the assessment at M3 is available then M3 score will be carried forward.
- Rule 3: If the assessment at M6 and M12 is not available in quiet conditions but available in noise then the score at M6 in noise will be used.
- Rule 4: In case of lost to follow-up or withdrawal of the informed consent for unknown reason a stochastic regression imputation will be used. This technique computes a regression equation that generates predicted values for the missing data. After a random error term generated from a normal distribution (with a mean of zero and a variance equal to the residual variance from the preceding regression analysis) is added to each predicted score and the resulting sum is used in place of missing values.
- Rule 5: In case of withdrawal not due to a failure of the implantation or complications the baseline will be imputed at month 6.
- Rule 6: In case of withdrawal due to major complications requiring new implantation, the worst observed score will be imputed.

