### **3.6.3 Handling of Missing Data**

#### **3.6.3.1 Imputation rules used in the primary analysis**

Rule 1: If the assessment at M6 is missing but a further assessment is available the missing assessment will be replaced by the next available data.

Rule 2: If the assessment at M6 and M12 is missing but the assessment at M3 is available then M3 score will be carried forward.

Rule 3: If the assessment at M6 and M12 is not available in quiet conditions but available in noise then the score at M6 in noise will be used.

Rule 4: In case of lost to follow-up or withdrawal of the informed consent for unknown reason a stochastic regression imputation will be used.

Rule 5: In case of withdrawal not due to a failure of the implantation or complications the baseline will be imputed at month 6.

Rule 6: In case of withdrawal due to major complications requiring new implantation the worst score (0%) will be imputed.

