## 6. Statistical analysis

### 6.1. Analysis of efficacy endpoint

The primary analysis of the primary efficacy endpoint will be performed on a subgroup of the FAS which consists of all English-speaking subjects.

Additional analysis with a replicate PPS will be performed on this subset of English-speaking patients.

The primary test is a one sample T-test performed on the change from baseline to 6 months after activation of the device. The value of the mean improvement under the null hypothesis is zero. The type I error ( $\alpha$ ) is set to 0.025 (one-sided).

The one sample Wilcoxon rank test will be applied in a sensitivity analysis. In case the normality assumption is strongly violated or in the presence of several outliers, the result of this sensitivity analysis will have a particular importance.

To further describe the benefit of the Neuro CIS in the studied population, the number of patients (as well as rate among the total population) showing a benefit of at least 20 percentage points in HINT-Q score after 6 months of device use when compared to baseline will be computed (table 8 with the related figure and table 16.6).

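### Rule 4 imputes a missing month-6 score with one random draw that the t-test then counts as observed, so the rule understates the standard error of the primary mean change

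*SAP*

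**What the plan says.** Protocol 3.6.3.1 lists six imputation rules for the primary analysis. For patients lost to follow-up, or who withdraw consent for an unknown reason, it says only that "a stochastic regression imputation will be used".

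SAP section 3 repeats the rule: "In case of lost to follow-up or withdrawal of the informed consent for unknown reason a stochastic regression imputation will be used". It then describes the method. A regression gives a predicted score. The random error is normal, "with a mean of zero and a variance equal to the residual variance from the preceding regression analysis". One such draw goes to each prediction, and "the resulting sum is used in place of missing values".

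SAP 6.1 then states: "The primary test is a one sample T-test performed on the change from baseline to 6 months after activation of the device". The type I error "is set to 0.025 (one-sided"), and the null value is zero. The analysis set is the English-speaking part of the FAS. SAP 4.1 keeps implanted patients in the FAS even if they have no post-operative data, so imputed scores enter the primary test.

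Neither document mentions repeated imputation, pooling or a variance correction. Neither names the regression predictors, a seed, a rule for draws outside 0-100%, or the order in which the six rules apply.

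**The concern.** A single draw carries two uncertainties that the t-test does not see. One is the random residual itself. The other is that the regression coefficients and residual variance are estimated from the observed patients but used as if known. The test divides by the square root of the full number of patients, as though every score had been measured. Its standard error is then too small whenever at least one patient is imputed this way. A different seed also gives a different mean, interval and p-value, and the plan fixes no seed.

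What is at stake is mainly the reported precision. The sample-size sections say that efficacy does not drive the size of the trial, so the useful efficacy result is the estimated change and its interval (SAP Table 8) rather than rejection of zero. SAP 6.1 also counts patients who gain at least 20 points. If Rule 4 scores enter that count, which the SAP does not exclude, a random number decides whether such a patient counts.

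**Working it through.** **Inputs from the documents.** 39 English-speaking patients, planned change 50 points, SD of change 25 (Protocol 3.6.1.4, SAP 1.3); null value 0, one-sided 0.025 (SAP 6.1). The only loss figure is 10%, for all subjects (Protocol 3.5.4).

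**Assumptions.** The number of Rule 4 patients, m, is varied. Scores are missing completely at random. The regression is of change on baseline, with correlation 0, -0.4 or -0.7.

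**The plan's own figure.** The power of the one-sample t-test follows a noncentral t with n - 1 degrees of freedom and noncentrality (50/25)√n. At one-sided 0.025 it is 90.9% for n = 5, 97.0% for n = 6 and 99.1% for n = 7. The stated 7 patients therefore give at least the stated 95% power; 6 would suffice.

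**Approximation by hand, correlation near 0.** Let k = n - m be the number observed. After imputation the mean is close to the observed mean plus (m/n) times the average of the m drawn residuals, so

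Var ≈ SD² × (1/k + m/n²).

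For m = 4: 625 × (1/35 + 4/1521) = 625 × (0.02857 + 0.00263) = 19.5, a true SD of 4.42. The t-test uses about 25/√39 = 4.00. The ratio is 4.00/4.42 = 0.907. The critical value 2.024 (38 df) thus acts like 2.024 × 0.907 = 1.835, which gives coverage of about 92.6% and one-sided error of about 3.7%. The same steps give coverage of 94.4% for m = 1, 93.8% for m = 2 and 89.8% for m = 8.

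**Simulation.** 40,000 trials per case for single imputation followed by the t-test. Ranges run over the three correlations:

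| Rule 4 patients of 39 | 95% CI coverage | One-sided type I error |
|---|---|---|
| 1 | 94.5-94.9% | 2.6-2.9% |
| 2 | 93.9-94.4% | 2.8-3.0% |
| 4 | 92.4-93.7% | 3.1-3.8% |
| 8 | 89.5-92.1% | 3.9-5.3% |

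A separate simulation over the same range of correlations gave coverage of 92.7-94.0% with four and 89.4-92.2% with eight, so the ranges are good to a few tenths of a point.

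**Comparison of methods, m = 4, correlation -0.4.**

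| Method | Mean half-width (points) | Coverage | One-sided error |
|---|---|---|---|
| Single draw (Rule 4) | 8.04 | 93.0% | 3.5% |
| Multiple imputation, 50 sets, Rubin's rules (8,000 trials) | 8.56 | 95.0% | 2.4% |
| Observed patients only | 8.53 | 95.0% | 2.4% |

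The Rule 4 interval is (8.56 - 8.04)/8.56 = 6% too narrow. It is also narrower than the interval from the observed patients alone. Its half-width stays near 8.04 whatever the number missing, because imputed scores count as measured.

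**Effect on the decision.** At the planned effect t = 50/(25/√39) = 12.5, a one-sided p of about 3 × 10⁻¹⁵. With only 31 observed patients p is still about 2 × 10⁻¹². With four imputed, the lower limit moves from about 50 - 8.0 = 42.0 to about 50 - 8.6 = 41.4.

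**The case against.** The strongest reply is that few patients may ever reach Rule 4. Rule 1 takes those with a later score, Rule 2 those with a month-3 score, Rule 3 those with a score in noise, and Rules 5 and 6 take withdrawals with certain known reasons. If the rules apply in the listed order, Rule 4 is left mainly with patients who have no post-activation score and leave without a known reason. The 10% figure covers every withdrawal in all three languages, so four of 39 is an assumption and eight has no source in the documents. This stands, and it is why the one- and two-patient cases are shown. It is not a full answer, because the order is not stated and Rules 2, 4 and 5 can apply to the same patient.

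The second reply is that other planned analyses expose the problem. The deletion scenario contains no Rule 4 draws, and its half-width is almost that of multiple imputation. The PPS requires study completion and is shown beside the FAS. A careful reader would therefore see a nearly correct interval. But the deletion, zero-score and tipping-point analyses vary the assumption about missing scores; none corrects the primary interval or p-value.

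A reader might also infer that any comparison with 20 points would be wrong. The documents plan no such test: 20 points appears as a clinically pertinent gain and as a descriptive count. At the planned effect the lower limit is above 41 under either method.

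Nor do these figures show that the primary test as a whole exceeds 0.025. They isolate Rule 4. Rule 5 imputes no change, and Rule 6 imputes zero (protocol) or the worst observed score (SAP). Both tend to pull the mean change down, and the net effect of all six rules was not assessed.

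**Conclusion.** The point holds for the variance under Rule 4. As written, the rule understates the standard error of the primary mean change whenever a patient falls under it, and the result cannot be reproduced from the plan. Coverage of the nominal 95% interval is about 93-95% with one or two such patients. With four it is about 92.5-94%, with one-sided error of about 3.0-3.8%; with eight, as a stress case, it is about 89.5-92%. These figures assume 39 patients, SD 25, scores missing completely at random and correlations from 0 to -0.7. Neither the correlations nor the counts are in the documents.

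A reader might conclude that the efficacy finding is in doubt. It is not: at the planned 50-point effect the conclusion against zero is untouched. The point concerns honest reported precision and reproducibility, and it should be corrected because the correction is cheap.

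**What to change.** In SAP section 3, and in Protocol 3.6.3.1 for consistency, replace the single draw in Rule 4 with multiple imputation:

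- Regress on baseline and any HINT-Q scores not already used by Rules 1 and 2. For most Rule 4 patients this will be baseline only.
- Draw the regression coefficients and residual variance as well as the residual.
- Use at least 50 imputations with a fixed, recorded seed.
- State how draws outside 0-100% are handled.
- Combine the means and variances by Rubin's rules, with t-based inference against zero at one-sided 0.025.
- State the order in which Rules 1-6 apply, so that each patient falls under one rule.
- State whether imputed scores enter the count of patients gaining at least 20 points.

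The cost is a little more programming in the SAS 9.4 already planned and a slightly wider interval: about half a point on the half-width with four such patients (8.56 - 8.04 = 0.52). No new data are needed. This does not address Rules 1-3, 5 and 6, which also insert single values.

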#### **3.5.5.2 Procedures to Assess Safety**

For the timing assessment please refer to the schedule of activities in section 3.5.5.4.

The PI shall be responsible for safety data collection.

The PI may plan any unscheduled consultations as needed to follow any adverse event.

All complications/adverse events are recorded and classified as major or minor complication by the investigator.

Serious Adverse Event or Major Complication (related or not related to the device) are those that are life-threatening (e.g. meningitis, death), those requiring hospitalization and/or resulting in disability or permanent damage (e.g. permanent facial nerve paresis, permanent chorda tympani syndrome, permanent vertigo/dizziness, persistent pain discomfort requiring device explant), those requiring revision surgery with or without re-implantation (e.g. device explant, surgery to prevent permanent impairment, large scalp necrosis, severe infection, electrode shifting, eardrum perforation, receiver positioning and cholesteatoma) and tinnitus, facial stimulation, pain that could not be alleviate by electrode deactivation; and other serious medical events.

Adverse Event or Minor Complication (related or not related to device) are those that resolve spontaneously without surgical intervention (e.g. wound infection treated by antibiotics; skin flap hematoma; transient or rising tinnitus; transient vertigo/dizziness; transient pain; transient chorda tympani syndrome; transient facial nerve palsy, and tinnitus, facial stimulation and pain that could be relieved by electrode deactivation), or with conservative medical management (medical complications, pre-existing conditions such otitis media).

All explanted devices returned to the manufacturer will be classified according the AAMI-CDV-4 CI86 guideline, and ditto for the non-implantable part (i.e. sound processor, accessories).

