### **Procedure for explanted device**

Explanted device must be recorded on the “Explanted Device Report Form”

Every explanted device shall be tested to determine the reason for device failure, and device explantation shall be reported as a serious adverse event and classified according to AAMI-CDV-4 CI86 guideline.

All explanted devices shall be returned to Oticon Medical for a formal evaluation and a report shall be made according to the criteria specified in the AAMI-CDV-4 CI86 guideline. It will be the responsibility of the Oticon Medical Vigilance System to determine the final classification of the device failure. Concurrent with any reporting to Oticon Medical of an explant, a report shall also be sent to the Local Competent Authority having relevant jurisdiction.

Complications may lead to device explantation, in such cases initial SAE reporting shall specify the reason:

- a. Explantation due to unrelated medical reasons, for example:

Device is removed to enable diagnostic or therapeutic procedures for conditions unrelated to the implantation or function of the device (e.g. MRI scanning need outside manufacturer specification, radiotherapy, surgical resection, etc.)

- b. Explantation for medical reasons associated with the device.

Any device explanted with medical symptoms that could be related to the device and/or caused by device malfunction, for example:

- Meningitis secondary to the cochlear implantation
- Infection near the receiver/stimulator, lead and/or electrodes
- CSF leakage due to the occurrence of CSF leakage secondary to cochlear implantation.
- Skin flap complication secondary to the cochlear implantation
- Allergic reaction to device components
- Dizziness due to occurrence of balance and other vestibular-related issues
- Pain or discomfort that cannot be eliminated with changes in program parameter settings (e.g. deactivating an electrode).
- Tinnitus appearing during device use or an increase in pre-existing tinnitus
- Extra-cochlear stimulation, stimulation at sites outside the cochlea (e.g. facial nerve, chorda tympani, or return electrode placement, etc.) secondary to cochlear implantation and resulting from medical related factors (e.g. anatomical malformation, otosclerosis, cochlea ossification, etc.)
- Electrode array misplacement during cochlear implantation
- Electrode migration out of the cochlea
- Implant migration/extrusion

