### **Record of modifications**

Version	Date	Comment
1.0	07/03/2018	First version
2.0	10/12/2019	Remove of ECAP analysis
3.0	27/01/2020	
Revision of the document:
 

- Correction of section 1.2, bullet points secondary objectives for consistency with PIC_07 version G, add “to evaluate the trend...speaking patients.

- Addition in section 1.4 tables references for better understanding of study plan

- Addition of section 5.7.3 “sustainability of the effect at 12 months” for consistency with PIC_07 version G section 3.6.2.4 “secondary analyses”.

- Addition of PPS for all analysis performed on FAS

- Addition of descriptive analysis on major complication related to device

- Addition of descriptive analysis for impedance and explanted patients

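### Rule 6 for a missing month-6 HINT-Q score imputes 0% in the protocol but an undefined worst observed score in the SAP, and neither document orders the six rules

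*SAP*

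**What the plan says.** Protocol section 3.6.3.1 and SAP section 3 each list six numbered rules for a missing month-6 (M6) HINT-Q score. The protocol heads them as the rules of the primary analysis.

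- **Rules 1 to 3 depend on which scores exist.** Rule 1 takes the next available score. Rule 2 reads "If the assessment at M6 and M12 is missing but the assessment at M3 is available then M3 score will be carried forward". Under Rule 3 the M6 noise score stands in when the quiet scores are missing.
- **Rules 4 to 6 depend on why the patient left.** Unexplained departures fall under Rule 4, which in the SAP begins "In case of lost to follow-up or withdrawal of the informed consent for unknown reason a stochastic regression imputation will be used". Departures with a benign reason fall under Rule 5, which in the protocol reads "In case of withdrawal not due to a failure of the implantation or complications the baseline will be imputed at month 6". For the most serious departures, the protocol's version of Rule 6 is "In case of withdrawal due to major complications requiring new implantation the worst score (0%) will be imputed". The SAP's version differs: "In case of withdrawal due to major complications requiring new implantation, the worst observed score will be imputed".

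The protocol's description of a major complication (section 3.5.5.2) includes "those requiring revision surgery with or without re-implantation". The FAS keeps every implanted patient, with or without postoperative data (SAP 4.1). The primary analysis is a one-sample t-test of the M6 change in the English-speaking part of that set.

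**The concern.** There are three defects in the rules that produce the primary estimate.

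1. **Two values for one trigger.** The protocol gives a number. The SAP's term could mean the lowest M6 score among the other patients, the patient's own lowest score (which may be the baseline), or the lowest score in the whole dataset.
2. **No order.** A patient who leaves after month 3 (M3) fits Rule 2 and also Rule 4, 5 or 6, according to the reason. The overlap is built in: Rule 2 needs M6 and M12 both missing, and SAP 5.1 counts a patient without the end-of-study visit as withdrawn.
3. **A gap.** Rule 5 excludes implant failure and complications, and Rule 6 requires new implantation. Withdrawal for failure or a major complication without new implantation therefore has no reason-based rule. If an earlier score exists, Rules 1 to 3 can credit hearing measured before the device was lost. If none exists, no rule applies although the FAS retains the patient. SAP Table 16.6 has a column for whether the device was replaced, so such patients are foreseen.

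The trial is open label, so a choice left open in the plan could be made with the scores in view. At stake are the reported mean gain and, to a smaller extent, the rate of patients gaining at least 20 points.

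**Working it through.** **Inputs from the documents.** English-speaking N = 39; planning gain 50 points, SD 25, one-sided 0.025 (Protocol 3.6.1.4, SAP 1.3). Cited baselines 11.3% and 14%, with 6-month scores of 78% (SD 24.9) and 75% (SD 28) (Protocol 2.1). Gain at 3 months 47.7 points (Protocol 3.6.1.4). Baseline at most 50% by eligibility (Protocol 3.4.3). Adult major complication rate 1.4 to 1.7% (Protocol 2.1), 2% in the sample size section, and 7.1% as the literature average over many years (Protocol 3.6.4).

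**The plan's own figure.** It states 7 patients for 95% power. The exact noncentral t calculation gives 97.1% at n = 6 and 99.1% at n = 7. The stated size is adequate and not in dispute.

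**Rule 2 against 0%, one patient.** The baseline cancels, so the shift in the mean is the M3 score divided by 39. The M3 score is taken as cited baseline plus 47.7:
- (11.3 + 47.7)/39 = 59.0/39 = 1.51 points
- (14 + 47.7)/39 = 61.7/39 = 1.58 points

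**Rule 2 against Rule 5.** Rule 5 sets the change to zero, so the shift is the M3 gain divided by 39: 47.7/39 = 1.22 points per patient. Protocol 3.5.4 tolerates 5 withdrawals in 55 before replacement; pro rata this is 5/55 × 39 = 3.5, so 3 to 4 patients. If all of them left after M3 for reasons unrelated to failure or complications (an assumption), the shift is 3 × 1.22 = 3.7 to 4 × 1.22 = 4.9 points.

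**SAP Rule 6 against protocol Rule 6, one patient.** The shift is the imputed score divided by 39.

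| Reading of worst observed | Imputed score | Shift (points) |
|---|---|---|
| Lowest in the dataset, if a zero is recorded (Protocol Appendix 7 provides for this) | 0 | 0 |
| Lowest M6 score of 38 others, bounded beta model | 7.9 to 13.5 | 0.20 to 0.35 |
| Lowest M6 score of 38 others, normal model | 16.1 to 25.0 | 0.41 to 0.64 |
| Own baseline, cited values | 11.3 to 14 | 0.29 to 0.36 |
| Own baseline, eligibility limit | 50 | 1.28 |

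The beta and normal rows are simulated from the cited 6-month means and SDs; the choice of distribution is an assumption.

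**Responder rate.** One patient is 1/39 = 2.6 percentage points, if imputed scores enter the count.

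**How many patients.** Expected major complications in 39: 39 × 1.4% = 0.5; 39 × 2% = 0.8; 39 × 7.1% = 2.8. These are ceilings for Rule 6, because only those who withdraw with the M6 score missing count.

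**The test against zero.** Give the other patients a mean gain of 50 and SD 25. Four patients imputed 0% from a baseline of 50 leave a mean gain of 39.7, t = 6.40, one-sided p = 8 × 10⁻⁸. Significance is lost only at about 13 of 39 patients imputed 0% if each had a baseline of 50, or about 25 of 39 at a baseline of 12.

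**The case against.** The best defence is that the numbering is itself a sequence. No text says so, but the reading is natural. It would not empty Rule 6, which would still cover patients withdrawn before any usable post-activation score, so it would be wrong to infer that Rule 6 is defeated. It would, however, credit the M3 gain to a patient withdrawn because the implant had to be replaced, which is hard to square with a rule that assigns such patients the worst score.

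The effects are also small. One patient moves the mean by less than half of its standard error of about 4.0 points (25/√39), and best-case, worst-case and tipping-point analyses are planned. That stands as to size. But those analyses bound the result; they do not say which value is the primary estimate.

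Two stronger readings are not supported. A reader might infer that Rule 6 was altered silently, because SAP version 3.0 records edits to the "bullet points secondary objectives for consistency with PIC_07 version G" and nothing on Rule 6. That record lists changes between SAP versions; if the wording dates from version 1.0, no entry would be expected, and earlier versions are not available. A reader might also see a conflict between the total-population denominator for responders in SAP 6.1 and the default in SAP section 3 that leaves missing data out. The section 3 text is only a default, and the specific rule already overrides it.

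**Conclusion.** Wrong as written, and it should be fixed. The two Rule 6 texts give different instructions for one trigger, the SAP term is undefined, no order is stated, and failures or major complications without new implantation have no reason-based rule.

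The consequence is limited to estimation. Rule order matters more per patient than the Rule 6 wording, except where that wording is read as a high own baseline. The largest total shift, 3.7 to 4.9 points, comes from Rule 2 against Rule 5 and rests on the assumption that every tolerated withdrawal is benign and falls after M3; the documents give no frequency for that. The M3 scores are built from different cited studies and are illustrations. A reader might infer that the efficacy conclusion is in doubt; the calculations show that it is not.

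**What to change.** In SAP section 3:

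1. Set Rule 6 to the protocol's 0%.
2. When M6 is missing, apply Rule 6 before Rules 1 to 3. Extend it to withdrawal for device failure or for a major complication without new implantation, whether or not the device was explanted. Minor complications are not included, nor is the protocol's category "Explantation due to unrelated medical reasons". A re-implanted patient who stays in the study is not a withdrawal and remains under Rule 1.
3. For all other withdrawals, state one order between Rule 2 and Rules 4 and 5. Rule 5 before Rule 2 is the less favourable to the device.

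The extension in step 2 goes beyond the protocol text and should be recorded in the SAP as an addition. The cost is wording and slight programming, with no new data. The reported mean gain may become slightly less favourable.
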